**INNOVATION:** MRI with hyperpolarized xenon-129 is a technique that is been used extensively in humans to detect lung ventilation function. Here we propose for the first time to use hyperpolarized xenon gas MRI to detect BAT. Xenon is an ideal BAT probe for several reasons: A) the solubility of xenon in fatty tissue is 10 times higher than in lean tissues or blood. This means that circulating xenon naturally diffuses into BAT, enabling adequate SNR for imaging. B) Xenon is an ideal blood perfusion tracer, and therefore ideally suited to detect the increase in blood flow to BAT that occurs during stimulation of BAT thermogenesis. C)

Because xenon is not intrinsic to biological tissue, HP  $^{129}\text{Xe}$  can produce background free maps of human BAT. D) The temperature sensitivity of lipid-dissolved xenon will enable us to directly measure BAT temperature and monitor thermogenic activity in real time.

*This research is innovative as it uses an entirely different approach to investigate BAT. To our knowledge we are the very first group to use hyperpolarized xenon gas to detect BAT mass and to have demonstrated HP xenon MR thermometry of fatty tissues.*

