**APPROACH: Aim1: Demonstrate BAT mass detection in human subjects.**

Our extensive preliminary studies in rodents have shown that, upon stimulation of BAT thermogenesis, an enhancement of more than 10-fold of the MR signal from xenon dissolved in BAT is observed. This enhancement is such that a background free map of this tissue can be obtained in just few seconds (Fig. 1). In addition, when compared to FDG-PET images of BAT, hyperpolarized xenon gas images were able to clearly show BAT in both lean and obese mice and, in the latter, with superior sensitivity (Fig.1b-d).

[figure not shown]
**Fig. 1** Detection of interscapular BAT by hyperpolarized xenon gas MRI (a-b) and FDG-PET (c-d) in a lean (a-c) and obese (b-d) animal. Hyperpolarized xenon gas is clearly more sensitive to the lipid-rich BAT of obese animals (b) than FDG-PET. In d) glucose uptake by BAT is substantially reduced, making it difficult to differentiate BAT from the surrounding tissue.

The broad aim of this proposal is to validate this completely new approach to detect BAT in humans. To this end we will perform HP  $^{129}\text{Xe}$ -MRI of BAT on a 3T clinical magnet using a dual tuned xenon/1H surface coil recently purchased for human BAT studies. The coil will be accurately located above the suprACLAVICULAR area to increase sensitivity to the xenon signal dissolved in the tissue beneath. Conventional  $^1\text{H}$  MRI, which will provide anatomical reference images, will be followed by HP  $^{129}\text{Xe}$  spectroscopy and imaging scans, similar to those used in our rodent studies. Before the acquisition of the xenon images, the subject will be asked to inhale a 1L bag of 100% hyperpolarized and enriched xenon from a Tedlar bag and to hold his breath for about 15-20s. During this time hyperpolarized xenon gas will diffuse from the lung airspaces to BAT in a perfusion-based manner. At the end of the 10 s from the beginning of gas inhalation we will trigger the acquisition of the MR image, which will last for about 10s. The

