same protocol will be followed during stimulation of BAT thermogenesis, which will be achieved by an MR compatible water cooling-blanket ( $\sim 15^{\circ}\text{C}$  circulating water temperature), which will be positioned on the lower abdomen/upper leg part of the subjects. The ability to detect BAT by hyperpolarized xenon gas relies on the enhancement in blood flow to this tissue that occurs during stimulation of thermogenic activity. The magnitude of this enhancement seems to be the same, irrespective of the species and of the modality of stimulation of BAT thermogenesis (NE injection of mild cold exposure). Therefore we expect to detect a similar enhancement in the MR signal from xenon dissolved in human BAT. In addition, the use of enriched xenon versus naturally abundant xenon will compensate for the possible loss in xenon polarization during blood transit time. Pre and post stimulation scans will be compared with Matlab to detect differences of more than 5% in the intensity of the dissolved phase xenon images. Detectable BAT volume will be calculated as the sum of pixels whose intensity rose by more than 5% during cold stimulation multiplied by the pixel volume ( $1 \text{ mm}^3$ ). Data will be analyzed using JMP Pro-9.0.0 software (SAS Institute). All P values presented will be two-tailed, and values less than 0.05 will be considered to indicate statistical significance. According to previous studies done in human brain and considering the increase in blood perfusion that occurs in BAT during cold stimulation as well as the higher solubility of xenon in fatty tissues, we expect to be able to obtain images with a resolution of  $0.3 \times 0.3 \text{ cm}$ , high enough to differentiate BAT from the surrounding tissues.

**Aim 2:** Demonstrate detection of BAT thermogenesis in humans.

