#### Hyperpolarized xenon-129 MRI:

Subjects will be positioned supine within the MR scanner. The dual tuned xenon/proton surface coil will be positioned above the supraclavicular area. After breathing normally for a few minutes, the subject will exhale completely to residual volume, and then inhale a 1-L volume of undiluted hyperpolarized xenon-129, followed by a breath-hold lasting from 10-15 s during and after which imaging will be performed. The subject will then exhale fully and breathe normal air. Xenon doses will be administered no less than 15 minutes apart. During the MRI exam, oxygen saturation, heart rate, and blood pressure will be continuously recorded. These parameters, along with respiratory rate and subjective symptoms, will also be assessed after each dose. Immediately after inhalation, the subject will also be asked to report any symptoms or effects from xenon.

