#### **-Enriched Xenon gas mixture (\$12,240)**

During the imaging study session the subject will receive two doses of 1L of HP Xenon, spaced 40 minutes apart (40 minutes is the minimum time required to produce a 1L of hyperpolarized xenon gas). For the spectroscopy study the subject will receive a total of 4 0.5L of hyperpolarized xenon every 20 minutes. Funds are therefore requested for 4800L of 1% enriched Xe (quoted at \$5,100 per 2000L cylinder by Linde specialty gas) that will lead to a total of 48L (2L per subject x 12 subjects) of enriched Xenon.

The cost of the non-enriched xenon gas as well as the cost of the other gases needed for the xenon polarizer will be covered in its entirety by the PI funds.

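### Aim 1 counts every pixel that rises more than 5% between two separate breath-holds, but no image alignment is described, so small movement of fat that has not changed can be counted as BAT

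*Combined protocol and SAP*

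**What the plan says.** The APPROACH section for Aim 1 states that "Pre and post stimulation scans will be compared with Matlab to detect differences of more than 5% in the intensity" of the dissolved-phase xenon images. Detectable BAT volume is then the "sum of pixels whose intensity rose by more than 5% during cold stimulation multiplied by the pixel volume", with the pixel volume given as 1 mm³. Later in the same paragraph, "we expect to be able to obtain images with a resolution of" 0.3 × 0.3 cm.

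The two images come from different breath-holds: the "same protocol will be followed during stimulation of BAT thermogenesis". The section headed Hyperpolarized xenon-129 MRI sets a general floor, "Xenon doses will be administered no less than 15 minutes apart". For the two imaging doses, the budget item on enriched xenon gives the specific figure, "spaced 40 minutes apart". The protocol does not say how long the subject is cooled before the second image.

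The signal is received by a dual-tuned xenon/1H surface coil over the supraclavicular area. Conventional 1H MRI comes before the xenon scans; its stated role is to supply pictures "which will provide anatomical reference images". For each dose the subject lies supine, empties the lungs to residual volume and inhales 1 L. Registration, motion correction, coil-sensitivity correction, an anatomical mask and a minimum cluster size are not mentioned anywhere.

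**The concern.** A per-pixel comparison assumes that a given pixel covers the same tissue in both images. Here the subject breathes freely between the images, is cooled, and takes a new breath. A small displacement at a border between fat and lean tissue brings fat signal into pixels that were lean before. Large edges are plausible because, according to the INNOVATION section, "the solubility of xenon in fatty tissue is 10 times higher than in lean tissues or blood". White fat has such borders too.

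The counting rule is one-sided. In tissue with no true change, a shift raises some edge pixels and lowers others, but the falls are never subtracted. The error therefore does not average out.

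BAT volume is the Aim 1 result. The study is also meant to supply the standard deviation of the signal increase for powering later trials, and the number of positive subjects out of 12. Movement artefact could enter all three, and no repeat scan without cooling is described that would expose it.

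**Working it through.** **The plan's own figure.** The plan gives no figure for movement. Its related figure is the number of positive subjects among 12 (section F, Number Justification). By the exact binomial, P(X ≥ 9 | 12, 0.9) = 0.974 and P(X ≥ 3 | 12, 0.5) = 0.981. The next cut-offs fall below 0.95 (≥ 10: 0.889; ≥ 4: 0.927), so the stated counts reproduce.

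**Inputs.** From the protocol: the 5% one-sided threshold, 3 mm in-plane resolution, and the 10-fold solubility ratio, used here as the upper end of signal contrast. Assumed: shifts of 0.5 to 3 mm, contrast down to 1.25:1, spherical depots of 10 and 20 mm diameter, and 3 mm cubic pixels (27 mm³).

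**One edge by hand.** Take a flat edge parallel to the pixel face, with contrast c:1. A shift of d mm fills a fraction d/3 of an adjoining lean pixel with fat, so its signal rises by (d/3)(c − 1).
- d = 1, c = 10: (1/3) × 9 = 300%.
- d = 1, c = 1.25: (1/3) × 0.25 = 8.3%, still above 5%.
- d = 0.5, c = 1.25: (0.5/3) × 0.25 = 4.2%, below 5%.
- Shift needed to reach 5%: 0.15/(c − 1) mm, which is 0.15 mm at 2:1 and 0.6 mm at 1.25:1.

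**Whole depot, no true change, no noise.** The same sphere is imaged twice on a 0.5 mm grid averaged to 3 mm pixels, with the second image shifted, over 12 random grid offsets. False volume = (pixels rising > 5%) × 27 mm³ ÷ true depot volume.

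| Contrast | Depot | 0 mm | 1 mm | 2 mm | 3 mm |
|---|---|---|---|---|---|
| 10:1 | 10 mm | 0% | 110% | 131% | 148% |
| 10:1 | 20 mm | 0% | 53% | 63% | 72% |
| 1.25:1 | 10 mm | 0% | 24% | 55% | 71% |
| 1.25:1 | 20 mm | 0% | 12% | 28% | 39% |

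At 2:1 the range over 1 to 3 mm is 75 to 121% (10 mm depot) and 37 to 59% (20 mm). A 0.5 mm shift gives 22 to 93% across 2:1 and 10:1. Repeat runs with other random offsets differ by several points; for the 10 mm depot at 10:1 they span 109–114%, 131–140% and 146–151%.

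A separate 2-D phantom on 1 mm pixels (radius 5 to 20 mm, contrast 2:1 and 10:1, with blur and coil decay) gives 16–117%, 23–139% and 27–158% of the disc area at 1, 2 and 3 mm, and 0 with no shift.

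**Whole depot, true enhancement (10:1 contrast).** With a 2-fold rise the count falls as the shift goes from 0 to 1, 2 and 3 mm: 162% to 148, 143 and 142% of true volume (20 mm depot), and 246% to 215, 203 and 209% (10 mm). With a 10-fold rise it falls from 166% to 158% and from 254% to 238%. The excess at zero shift arises because edge pixels only partly filled by BAT are counted whole.

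**Coil distance.** On the axis of a loop of radius a, sensitivity varies as (1 + z²/a²)^(−3/2), so the relative slope is 3z/(a² + z²). With assumed a = 5 cm and z = 3 cm, the slope is 9/34 = 0.265 per cm. A 5% change then needs ln(1.05)/0.265 = 0.184 cm, or 1.8 mm, for receive only. It is half that, 0.9 mm, for transmit-receive at small flip angle. Loop radii of 3 to 7.5 cm at the same depth give about 0.5 to 3.5 mm over both modes. Movement towards the coil raises the signal; movement away lowers it.

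**Effect on the count of positives.** If true prevalence is 50% and a fraction f of BAT-negative subjects is falsely positive, the positive rate is 0.5 + 0.5f. P(≥ 9 of 12) is then 0.073 at f = 0, 0.282 at f = 0.25 and 0.649 at f = 0.5. The values of f are assumed, because the protocol does not define how much volume makes a subject positive.

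**The case against.** The protocol does control position to some degree. Each dose is taken supine, from residual volume, with a fixed 1 L. The blanket lies on the lower abdomen and upper legs, away from the coil. Repeating the same protocol during cooling could be read to include a second 1H scan. This is a short feasibility proposal that leaves the Matlab routine undescribed, so silence on alignment is not a decision against it. All of this stands. It reduces the likely displacement and limits the claim to what is described. It does not supply an alignment step, and neither 1H imaging in the cold condition nor its use for registration is stated.

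Several stronger readings are tempting but not supported:
- A reader might infer that misalignment always adds volume. It does so for tissue that does not enhance; with true enhancement the count can fall, and coil distance can act in either direction.
- A reader might take 1 to 3 mm of movement as established. The documents give no displacement, and nothing in them shows that cooling causes movement.
- A reader might join the 15-minute floor to the 40-minute spacing and call that the cooling time. For the imaging doses the figure is 40 minutes, and dose spacing is not cooling duration.
- A reader might treat 10:1 as the image contrast. It is a solubility ratio. Delivery depends on perfusion, so poorly perfused white fat may show much less contrast; hence the range down to 1.25:1.

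**Conclusion.** The concern holds conditionally. The written rule counts rises only, compares separate breath-holds, and is given without an alignment step. If tissue moves by 1 to 3 mm, fat with no true change yields a false BAT volume of about 12 to 72% of a 20 mm depot and 24 to 148% of a 10 mm depot, against 0% with no shift. At 0.5 mm the effect is still material at contrasts of 2:1 and above, while a flat edge at 1.25:1 stays under the threshold.

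These sizes rest on assumed displacement, contrast, depot shape and cubic 3 mm pixels, and they exclude noise. The coil effect also rests on assumed geometry and has no fixed sign. The result does not show that the study will overstate BAT in every subject. It shows that the endpoint as written cannot separate small movement from a thermogenic response at fat edges, which is reason enough to specify alignment before scanning.

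**What to change.** In the Aim 1 APPROACH text:
1. Acquire a short 1H image with the same dual-tuned coil next to each xenon breath-hold, at the same lung inflation.
2. Register the cold xenon image to the pre-cooling image through these 1H images before any pixel comparison.
3. Correct for coil sensitivity.
4. Restrict the count to a supraclavicular fat mask defined on the 1H images.
5. Report residual displacement for each pair and prespecify the tolerance beyond which a pair is not evaluable, justified by its simulated effect on the volume. One third of a pixel (1 mm) is too loose: by the table above it still allows 12 to 53% of a 20 mm depot and 24 to 110% of a 10 mm depot.

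The cost is a few minutes of 1H scanning with the coil already in place, a registration step, and the possible loss of a scan pair out of 12.

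Registration does not correct noise, dose-to-dose differences in polarization, or partial-volume counting at the 5% threshold. With no movement and no true change, about 24% of pixels would rise more than 5% at an assumed signal-to-noise ratio of 20, and 4% at 50. The threshold therefore needs its own justification, for example from repeat scans without cooling.

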Dynamic spectroscopy data have shown the possibility to track BAT temperature over time by measurement of the chemical shift of lipid-dissolved xenon. We demonstrated for the first time MR thermometry by hyperpolarized xenon gas. This method is based on the temperature dependence of the chemical shift of lipid dissolved xenon, which we measured for the first time *in vivo* to be  $-0.2 \text{ ppm}^{\circ}\text{C}$ , (Fig 2.a), i.e. 20 times larger than that of water protons currently used for MR thermometry in lean tissues. This higher sensitivity of lipid-dissolved xenon to temperature, coupled with the lower gyromagnetic ratio of xenon (which makes xenon less sensitive to possible magnetic field in homogeneities present in fatty tissues), allowed us to detect BAT thermogenic activity in mice (Fig.2.b). To this end we will acquire dynamic spectroscopy data from xenon dissolved in BAT during stimulation of BAT thermogenesis by mild cold exposure. During these scans we will track the resonance frequency of lipid-dissolved xenon to detect changes in BAT temperature during thermogenic activity. Although in humans we expect temperature changes less than  $2^{\circ}\text{C}$ , the high sensitivity of xenon to temperature and the narrow line width can allow us to detect changes as small as  $0.2^{\circ}\text{C}$ .

**Fig.2** a) Linear temperature shift of the lipi-dissolved xenon frequency as acquired *in vivo* in an obese mouse. b. Thermogenic activity as detected by hyperpolarized xenon gas. The graph shows the resonance frequency shift of lipid-dissolved xenon and the corresponding shift in BAT temperature right after injection of NE.

For these studies the subject will inhale 4 doses of 1L each of xenon during mild cold exposure, achieved with a water cooling blanket. After inhalation, the subject will be asked to hold his breath for 15-20 seconds, during which we will trigger the acquisition of xenon spectra. The spectra will then be fitted with homemade Matlab routines to extract lipid-dissolved xenon resonance frequency that will be used to detect any change in BAT temperature.

The change in BAT temperature will then be analyzed as function of BMI to establish whether or not there is an association between BMI and BAT temperature increase (Pearson correlation and Spearman correlation coefficient calculation).

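### The Aim 1 volume rule counts any dissolved-phase xenon pixel that rises by more than 5%, so a circulatory rise in vessels or muscle would be summed as BAT

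*Combined protocol and SAP*

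**What the plan says.** Under APPROACH, Aim 1, the scans before and during cooling are compared "to detect differences of more than 5% in the intensity of the dissolved phase xenon images". Detectable BAT volume is the "sum of pixels whose intensity rose by more than 5% during cold stimulation", multiplied by the pixel volume. No lipid frequency, fat mask, or exclusion of vessels or muscle is attached to this rule.

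The same section sets the timing and the delivery mechanism. On timing: "At the end of the 10 s from the beginning of gas inhalation we will trigger the acquisition of the MR image". Acquisition takes about 10 s, so the window is roughly 10 to 20 s. On delivery, it states that "hyperpolarized xenon gas will diffuse from the lung airspaces to BAT in a perfusion-based manner". It also plans proton images for anatomy and xenon spectroscopy in the same session, but uses neither in the count. Its only stated ground for telling BAT from its neighbours is an expected in-plane resolution of 0.3 x 0.3 cm.

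INNOVATION states that "the solubility of xenon in fatty tissue is 10 times higher than in lean tissues or blood". For Aim 2 the spectra are fitted to "extract lipid-dissolved xenon resonance frequency", so the authors do distinguish the lipid compartment there.

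**The concern.** The dissolved phase is a wider category than lipid-dissolved xenon. As worded, it takes in xenon carried in blood and held in muscle and other lean tissue under a supraclavicular coil. Cooling can alter circulation outside BAT. If such a change raises a vessel or muscle pixel by more than 5%, the rule adds that pixel to BAT volume. The volume is an unweighted count, so a 6% rise in muscle contributes as much as the rise of more than tenfold that the authors saw in rodent BAT.

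This is real signal from another compartment. It would remain in noise-free, dose-matched and perfectly aligned images. At stake are the volume itself and, if a positive subject is defined through this rule (the plan does not say), the count of positives out of 12.

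**Working it through.** **1. The plan's own figure.** The sample-size text (end of APPROACH, and section F) expects at least 9 of 12 positives at 90% prevalence and at least 3 of 12 at 50%. Exact binomial: P(X >= 9 | 12, 0.9) = 0.974 and P(X >= 3 | 12, 0.5) = 0.981. Asking for one more positive gives 0.889 and 0.927. The figures 9 and 3 therefore reproduce. They assume that every subject is classified without error.

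**2. Inputs for the uptake check.**
- Solubility ratio of fat to blood: L = 10 (INNOVATION). The same sentence treats lean tissue and blood alike, so L = 1 for lean tissue.
- Time: t = 10 to 20 s (Aim 1).
- Tissue flow F: not in the documents. Assumed 0.05-0.5 mL/g/min, then extended to 5.
- Model, also assumed: single compartment, constant arterial xenon, no transit delay, no loss of polarization in tissue, 1 g of tissue taken as 1 mL.

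Formula: tissue/arterial concentration = L x (1 - exp(-F x t / L)).

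**3. What tenfold solubility adds in this window.** Compare L = 10 with L = 1 at the same flow.

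| F (mL/g/min) | t (s) | L = 10 | L = 1 | Gain |
|---|---|---|---|---|
| 0.05 | 10 | 0.0083 | 0.0083 | 0.4% |
| 0.05 | 20 | 0.0167 | 0.0165 | 0.8% |
| 0.5 | 10 | 0.083 | 0.080 | 4% |
| 0.5 | 20 | 0.165 | 0.154 | 8% |
| 5 | 10 | 0.80 | 0.57 | 41% |
| 5 | 20 | 1.54 | 0.81 | 89% |

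When t is short against L/F, uptake is close to F x t whatever the solubility. At F = 0.5, L/F = 10/0.5 = 20 minutes; the window is 10 to 20 seconds.

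**4. Lean tissue against the 5% limit.** With L = 1, t = 20 s and assumed baseline flows of 0.02-0.3 mL/g/min, a 6% flow rise gives a signal rise of 5.7-6.0%, which is counted. A 5% flow rise gives 4.7-5.0%, which is not. Example at F = 0.1: (1 - exp(-0.106 x 20/60)) / (1 - exp(-0.1 x 20/60)) = 0.0347/0.0328 = 1.059.

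**5. Pixels that contain a vessel.** Let a share v of the pixel be arterial blood (concentration 1) and the rest fat at concentration c. Signal = v + (1 - v)c, and a 5% rise needs v to grow by 0.05 x signal/(1 - c). At 15 s and v = 5%:
- F = 0.1 gives c = 0.025 and signal 0.05 + 0.95 x 0.025 = 0.074. Blood supplies 68% of it, and v need only move from 5% to 5.4%.
- F = 1 gives c = 0.247. Blood supplies 18%, and v must move from 5% to 6.9%.

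**6. Effect on the positive count, illustration only.** Take true prevalence 50% and let a share q of BAT-negative subjects be called positive, so p = 0.5 + 0.5q. P(X >= 9 of 12) is 0.07 for q = 0, 0.28 for q = 0.25 and 0.65 for q = 0.5. The documents give no value for q.

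**The case against.** A reader might infer that vessels are counted because blood holds far more xenon than fat this early. With the formula above, arterial blood exceeds BAT by 120-fold at 10 s and 60-fold at 20 s for F = 0.05, and by 12-fold and 6-fold for F = 0.5. The documents do not support that inference. The rule acts on relative rise, so a pixel equally bright in both scans changes by 0% and is never counted. Nor is the ratio secure. If flow reached 5 mL/g/min it would be 1.25 at 10 s and 0.65 at 20 s, and the authors do expect a large rise: in rodents "an enhancement of more than 10-fold of the MR signal from xenon dissolved in BAT is observed". Venous blood may also hold less xenon than arterial blood at this stage. All of this stands, and the point does not rest on brightness.

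It would also overstate matters to say that the plan relies on solubility for specificity. INNOVATION links solubility to adequate signal and derives freedom from background from xenon being foreign to tissue. Aim 1 names increased blood flow as the basis of detection. That is fair, but xenon's absence from native tissue does not remove inhaled xenon from blood or muscle, and flow is not unique to BAT.

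The scans are described as similar to the rodent ones, which gave background-free maps, so frequency-selective imaging may be intended. Its absence from the text does not prove its absence from the method, and a sentence would settle it. The rule as written still lacks it.

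Finally, the planned SD is for the increase in BAT signal and for temperature. A claim that the SD of volume is contaminated has no footing in the plan.

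**Conclusion.** The point holds as a defect in a stated rule: any dissolved-phase pixel that rises by more than 5% is labelled BAT, whatever its tissue. A lean-tissue flow rise of about 6% is enough to cross the limit under the uptake model. Solubility gives little protection at 0.05-0.5 mL/g/min (0.4-8%) and more at 0.5-5 mL/g/min (4-41% at 10 s, 8-89% at 20 s). The flows are assumptions.

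The documents do not show that vessels or muscle will rise by more than 5% under this cooling, or how often. The size of the overcount is unknown and could be small. The 10-20 s window comes from Aim 1. The breath-hold is 15-20 s there and 10-15 s in the Hyperpolarized xenon-129 MRI section, and these passages must be reconciled. The finding does not depend on which is used.

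**What to change.** In the Aim 1 analysis text, apply the comparison and the volume sum to the lipid-dissolved resonance, located with the xenon spectroscopy already planned for the session. Alternatively or in addition, restrict the count to pixels identified as fat on the proton images already acquired, excluding visible vessels and muscle. If only total dissolved-phase images can be made, report the result as a change in dissolved xenon signal and not as BAT volume. If the lipid signal is already selected, say so.

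No extra dose or scan is needed. Selective excitation loses some signal or speed, and masking adds some work. The documents do not show how cleanly blood and lipid signals separate in humans. At the blood-to-BAT ratios of 6 to 120 above, 1% leakage from a blood-filled pixel would equal 6-120% of a BAT pixel's signal, which is a reason to keep the proton mask available. Lipid selection also still includes white fat, unless white fat responds differently to cooling, and the report should say so.

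### The Aim 1 rule that counts every pixel rising by more than 5% has no noise limit, counting mask or dose scaling, so the plan does not show that it can separate BAT from noise or from a difference between two xenon doses

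*Combined protocol and SAP*

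**What the plan says.** All of the rule stands in the Approach, Aim 1. One xenon image taken before cooling is set against one taken during cooling: "Pre and post stimulation scans will be compared with Matlab to detect differences of more than 5% in the intensity" of the dissolved-phase images. The outcome follows from that: "Detectable BAT volume will be calculated as the sum of pixels whose intensity rose by more than 5% during cold stimulation", and this count is "multiplied by the pixel volume", given as 1 mm³. The same paragraph says "we expect to be able to obtain images with a resolution of" 0.3 x 0.3 cm.

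On image quality, the Innovation section offers only "enabling adequate SNR for imaging", without a number. It adds that xenon "can produce background free maps of human BAT", and the Approach says of the rodent work that "a background free map of this tissue can be obtained in just few seconds". The expected effect is large: more than 10-fold in rodents, with a similar rise expected in humans.

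Imaging is done "using a dual tuned xenon/1H surface coil recently purchased for human BAT studies", placed over the supraclavicular area. Proton anatomical images and xenon spectroscopy are also planned for Aim 1. None of these is linked to the pixel count. The budget note on enriched xenon gives two 1 L doses per imaging session, 40 minutes apart, and states that a litre takes at least 40 minutes to produce.

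The available text gives no source for 5%, no noise SD, no repeat scan without cooling, no step to align the two images, and no correction for delivered volume or polarization.

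**The concern.** Two images of unchanged tissue differ by chance. The rule adds pixels that rise and does not subtract pixels that fall, so chance rises do not cancel. A fixed 5% cut is strict where the signal is far above noise and very loose where it is near noise. The background-free maps that the plan expects would put pixels outside BAT in the loose region.

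The two images also come from two inhalations. If the second dose gives more signal, the whole image brightens and unchanged tissue is counted. If it gives less, the count shrinks. The rule cannot tell either case from a response to cooling.

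At stake is the Aim 1 volume. The signal increase that is meant to help power future trials would also be affected if it were averaged over pixels selected because they rose. The plan does not say that it will be.

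**Working it through.** **Plan's own figure.** The plan gives no error rate for the 5% rule. Its sample-size statement does reproduce: for 12 subjects, P(at least 9 positive) = 0.974 at 90% prevalence and P(at least 3) = 0.981 at 50%. The plan does not define a positive subject by the pixel count, so those figures are not in question here.

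**Inputs.** The cut (ratio above 1.05) and the single before/during pair come from the Approach, Aim 1. Assumed, because the documents do not give them: magnitude images, independent noise of equal SD in both images, SNR = signal divided by that SD, and the dose ratio g (second dose signal over first).

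**Signal-free pixels.** For magnitude noise, P(second > 1.05 x first) = 1/(1 + 1.05²) = 1/2.1025 = 47.6%, if such pixels are counted.

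**Unchanged signal pixels.** P(pass) = Φ[(g − 1.05) x SNR / √(1 + 1.05²)], with √2.1025 = 1.45. A simulation of 2 million pairs with magnitude (Rician) noise agrees to within rounding.

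| Assumed SNR, g = 1 | 5 | 10 | 20 | 30 | 50 | 100 |
|---|---|---|---|---|---|---|
| Unchanged pixels counted as BAT | 43% | 36% | 24% | 15% | 4% | 0.03% |

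**SNR needed with equal doses.** SNR = z x 1.45/0.05 = 29z.
- For 5% false pixels: 29 x 1.645 = 48.
- For 1%: 29 x 2.326 = 67.
- For 0.13% (3 SD): 29 x 3 = 87.

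**Unequal doses.**
- SNR 20, g = 1.10: Φ(0.05 x 20/1.45) = Φ(0.69) = 75%.
- SNR 20, g = 0.90: Φ(−0.15 x 20/1.45) = Φ(−2.07) = 2%.
- SNR 100, g = 1.03: Φ(−0.02 x 100/1.45) = Φ(−1.38) = 8%, against 0.03% with equal doses. High SNR therefore does not remove the dose problem.

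**Direction of the error with equal doses.** Let f be the BAT share of counted pixels, q the share of BAT pixels that pass and p the share of unchanged pixels that pass. The count is too high when f is below p/(p + 1 − q).
- Rise of about 10-fold: q is essentially 1 (99.8% even from SNR 0.5), so the count is too high unless nearly every counted pixel is BAT.
- SNR 5, 1.3-fold rise: p = 0.43, q = 0.80, so the crossover is 0.43/(0.43 + 0.20) = 68%. Above that share the count is too low.
- SNR 10, 1.1-fold rise: p = 0.36, q = 0.63, so the crossover is about 50%. For rises smaller than this it drops below half.

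**Pixel volume.** A 0.3 x 0.3 cm pixel covers 9 mm². It has a volume of 1 mm³ only with a slice 1/9 = 0.11 mm thick, or if the counted pixels are interpolated. The text does not say which.

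**The case against.** The best defence is the expected effect. If BAT brightens about 10-fold, it will be obvious, and the coil position and anatomical images tell the reader where to look. That defends sensitivity. It does not address unchanged pixels that also pass, because neither the coil position nor the anatomical images restrict the count.

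Several other objections stand and limit the point:

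- A reader might infer that the rule cannot work at all. The documents do not support that: at SNR 100 with matched doses only 0.03% of unchanged signal pixels pass. What can be said is that the plan does not show that those conditions hold.
- A reader might infer that noise always inflates the count. It does not; the crossovers above show when the count is too low.
- The 47.6% figure applies only to magnitude images in which empty pixels are counted. The plan states neither.
- Every dose difference used here is assumed. That the two doses are produced separately is inferred from a budget note on production time.
- The 1 mm³ figure may be an interpolated pixel. The documents support only that it must be reconciled with the stated resolution, not that the volume is wrong in a given direction.
- Aim 1 is a feasibility aim, and saved images can be analysed again. But a limit chosen after the images are seen is not neutral, and a dose reference not recorded at the scan cannot be recovered.

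**Conclusion.** The point holds in a limited form and should be fixed before scanning. As written, the rule can count unchanged tissue as BAT, and nothing in the plan shows how often. Depending on SNR alone, the share of unchanged signal pixels counted runs from 43% (SNR 5) to 0.03% (SNR 100). A 10% dose difference at SNR 20 moves it from 24% to 75% or 2%. With equal doses the count is too high if rises are large or if BAT, rising by 10% or more, fills a minority of counted pixels; it can be too low if small rises fill most of the counted area.

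These sizes rest on assumed SNR, dose ratios and noise model, so the actual error is unknown. A reader might go further and conclude that the statements about 9 and 3 positive subjects are wrong, or that the SD for future trials is biased. The plan ties neither to this count, so neither conclusion is supported.

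**What to change.** 1. Count only inside a supraclavicular fat mask drawn on the planned 1H images before the xenon images are viewed, after checking that the two xenon images are aligned.
2. Replace the 5% cut with a pre-specified noise-based limit at the acquired resolution, for example rise > 3 x √(σ_pre² + σ_post²). Measure σ in a signal-free region and correct it for magnitude noise (for one channel, divide the background SD by about 0.655). With matched doses about 0.13% of unchanged pixels then pass, at SNR 5 and SNR 20 alike.
3. Scale the two images for dose if a reference exists. Candidates are a bag polarization measurement, or the Aim 1 xenon spectroscopy if it shares a breath with the image and yields a signal that cooling does not affect. At SNR 20 with a 10% stronger second dose, 5.6% of unchanged pixels pass the limit in step 2 unscaled and 0.13% scaled. Without a reference, state that dose differences are uncorrected and limit the conclusion.
4. Estimate the signal increase and its SD over the whole mask, not over pixels selected for rising.
5. Multiply the count by the actual volume of the counted pixel, and reconcile 1 mm³ with 0.3 x 0.3 cm.

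**Cost.** Steps 1, 2, 4 and 5 are analysis wording and Matlab work, with no new scans, doses or subjects. Step 3 depends on a reference that the documents do not confirm.

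**Downside.** Small rises at low SNR are missed pixel by pixel: a 1.3-fold rise is detected 2%, 19% and 89% of the time at SNR 5, 10 and 20. A 10-fold rise is detected 99.9% of the time from SNR 1 but only 35% from SNR 0.5. Step 4 recovers part of this when doses match or are scaled. With 100 independent pixels (assumed) at SNR 5, a 1.3-fold rise exceeds 3 SE of the mask mean 99% of the time if it fills half the mask, but only about 3% if it fills a tenth.
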